8.6. Pharmacodynamics

Whole blood samples will be collected for measurement of serum total and free properdin concentrations, CAP activity, CCP activity, and potentially other measures of complement activation as specified in the SoA (Section 1.3). Additional samples may be collected at additional time points during the study if warranted and agreed upon between the Investigator and Alexion. The total blood volume will not exceed the blood volume limit for healthy participants (Section 8.2.4). The timing of sampling may be altered during the course of the study based on newly available data (eg, to obtain data closer to the time of peak plasma concentrations) to ensure appropriate monitoring.

Instructions for the collection and handling of biological samples will be provided by Alexion. The actual date and time (24-hour clock time) of each sample will be recorded.

Samples will be used to evaluate the PD of ALXN1820. Samples collected for analyses of ALXN1820 concentration may also be used to evaluate safety or efficacy aspects related to concerns arising during or after the study. Unused samples may be retained for a period of up to 5 years to perform additional assessments as necessary.

8.7. Genetics

Genetics are not evaluated in this study.

8.8. Biomarkers

Collection of samples for biomarker research (eg, exploratory) is also part of this study. See Section 10.5, Appendix 5 for details.

The following samples for biomarker research are required and will be collected from all participants in this study as specified in the SoA (Section 1.3):

- Blood
- Urine

Samples will be collected for testing that may include, but are not limited to, markers of complement dysregulation (eg, Factor Ba), vascular inflammation (eg, soluble tumor necrosis factor receptors), and endothelial activation/damage (eg, soluble vascular cell adhesion molecule-1, thrombomodulin).

8.9. Immunogenicity

Antibodies to ALXN1820 (ADAs) will be evaluated in whole blood samples collected from all participants according to the SoA (Section 1.3)

Serum samples will be screened for ADAs that bind to ALXN1820. If the screen is positive, the sample will be analyzed using a confirmatory ADA assay and the titer of confirmed positive samples will be reported. The detection and characterization of antibodies to ALXN1820 will be performed using a validated assay method by or under the supervision of the Sponsor. Samples may be further characterized to determine the titer and the presence of neutralizing antibodies (as an exploratory analysis) if deemed necessary. Additional samples may be collected during the study if warranted and agreed upon between the Investigator and the Sponsor.

Subjects who remain ADA positive for ALXN1820 at the end of the study will be requested return to the clinic for blood collection to assess ADA for up to a year following the end of the study or until ADA returns to baseline levels (for a maximum of 3 follow-up visits).

The actual date and time (24-hour clock time) of each sample will be recorded. Samples may be banked for a period of up to 5 years in order to perform additional safety assessments, as necessary.

Detailed instructions on the procedure for collecting, processing, storing, and shipping serum samples for immunogenicity analysis will be provided in the laboratory manual.

8.10. Medical Resource Utilization and Health Economics

Medical resource utilization and health economics data will not be evaluated in this study.

9. STATISTICAL CONSIDERATIONS

9.1. Statistical Hypotheses

Not applicable.

9.2. Sample Size Determination

The sample size is based on PK considerations. A sample size of up to 80 participants (8 participants per cohort) will be enrolled.

9.3. Populations for Analyses

For purposes of analysis, the following populations are defined:

Population	Description
Safety	All participants who receive at least 1 dose of study drug
Pharmacokinetic	All participants who receive at least 1 dose of the study drug and have at least 1 post-dose PK sample.
Pharmacodynamic	All participants who receive at least 1 dose of study drug and who have evaluable properdin concentration, CAP or CCP activity data
Immunogenicity	All participants who have a predose and at least 1 postdose ADA sample collected

Abbreviations: ADA = antidrug antibody; CAP = complement alternative pathway; CCP = complement classical pathway; PK = pharmacokinetic(s).

9.4. Statistical Analyses

In general, descriptive statistics for continuous variables will include number of nonmissing values, arithmetic mean, standard deviation, median, minimum, and maximum. Descriptive statistics for PK parameters will include number of observations, arithmetic mean, standard deviation, arithmetic coefficient of variation (% CV), median, minimum, maximum, geometric mean, and geometric %CV. Categorical variables will be summarized using percentages and frequency counts, by cohort and time point.

A statistical analysis plan (SAP) will be developed and finalized before first data cutoff/database lock and will further describe the participant populations to be included in the analyses, and procedures for accounting for missing, unused, and spurious data as appropriate. This section is a high-level summary of the planned statistical analyses of the primary and secondary endpoints.

9.4.1. Efficacy Analyses

No efficacy analyses will be performed for this study.

9.4.2. Safety Analyses

The primary endpoint for the study is safety and tolerability.

All safety analyses will be performed on the Safety Population and will be reported by each cohort and treatment arm (ie, ALXN1820 or placebo). In addition, healthy participants on placebo treatment will be pooled together across cohorts.

Safety analyses will include an analysis of all treatment-emergent AEs, ECGs, clinical laboratory data, physical examinations, and vital sign measurements using descriptive statistics. No inferential statistical analyses are planned on the safety parameters of this study. The prevalence of AEs and SAEs will be summarized, by SOC and Preferred Term for each cohort and treatment arm and overall, within each treatment arm, and by relationship to study drug. Adverse events will also be summarized by cohort and treatment arm, and overall, within each treatment arm, and by severity. Serious AEs and AEs resulting in withdrawal from the study will be listed. Participants having multiple AEs within a category (eg, overall, SOC, Preferred Term) will be counted once in that category. For severity tables, a participant's most severe event within a category will be counted.

Changes from baseline in vital sign measurements and laboratory assessments (eg, chemistry, cell blood count with differential, and urinalysis) will be summarized by each cohort and treatment arm, and overall within placebo treated healthy participants. Laboratory parameter values will be graded according to the Common Terminology Criteria for Adverse Events (CTCAE, v5.0, published 27 Nov 2017). Shift tables by cohort and treatment arm will be produced for these laboratory parameters. These tables will summarize the number of participants with each baseline grade relative to the reference ranges and changes to the worst highest grade assessed postdose during the study.

All concomitant medications will be coded using the World Health Organization Drug Dictionary, and the frequency and percentage of concomitant medications will be summarized.

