15. Participation (ie, last protocol-required study visit) in a clinical study within 90 days or 5 half-lives of the investigational agent, whichever is longer, before initiation of dosing on Day 1.
16. Participation in more than 1 clinical study of a mAb, or participation (ie, last protocol-required study visit) in a clinical study of a mAb within the 6 months or 5 half-lives of the mAb, whichever is longer, prior to Screening, during which the participant was exposed to the active study drug.

Diagnostic assessments

17. Positive or indeterminate QuantiFERON[®]-TB test indicating possible TB infection.
18. Presence of fever (confirmed body temperature $> 37.6^{\circ}\text{C}$) within 14 days prior to dosing on Day 1.
19. Serum creatinine greater than the upper limit of normal (ULN) of the reference range of the testing laboratory at Screening or on Day -1.
20. Alanine aminotransferase (ALT) or aspartate aminotransferase (AST) $> \text{ULN}$ of the reference range of the testing laboratory at Screening or $> 1.5 \times \text{ULN}$ of the reference range of the testing laboratory on Day -1.
21. Any clinically significant abnormal hematological parameters (per the Investigator's discretion with agreement of the Sponsor).
22. Positive urine drug toxicology screen at Screening or on Day -1.
23. Alcohol consumption within 48 hours prior to study drug administration or positive alcohol breath test on Day -1.
24. Donation of plasma within 7 days prior to dosing on Day 1. Donation or loss (excluding volume drawn at Screening) of more than 400 mL of blood within the last 16 weeks prior to dosing on Day 1.

Other Exclusions

25. Female participants who are pregnant or breastfeeding.
26. Participants who are in intimate and prolonged contact with (defined as living under the same roof, living in dormitory-style accommodations, or providing personal care to) people younger than 2 years of age or older than 65 years of age, or who are either immunocompromised or have one of the following underlying medical conditions: anatomic or functional asplenia (including sickle cell disease); congenital complement,

properdin, factor D, or primary antibody deficiencies; acquired complement deficiencies (eg, those receiving eculizumab); or HIV.

27. Participants who are one of the following:
 - a. Professionals who are exposed to environments of greater risk for meningococcal disease.

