All summaries will be based on results in SI (standard international system of units) units and will be output in the order listed above.

Toxicity grading following the NCI CTCAE grades version 5.0 will also be derived for laboratory variables where applicable (see list below). Note, where gradings require investigator/clinical input, this will not be considered and only the numeric criteria will be used for the assignments. If this results in the criteria for more than one grade being met, the highest (worst) CTCAE grade will be assigned. For creatinine only, the criteria based on the upper limit of normal (ULN) will be used (changes compared to the baseline value will not be used), e.g., CTCAE defines Grade 1 as $> \text{ULN} - 1.5 \times \text{ULN}$ or $> 1 - 1.5 \times \text{baseline}$. Only the $\text{ULN} - 1.5 \times \text{ULN}$ criterion will be used (and not the baseline criterion).

This document is confidential.

The following parameters are CTCAE gradable:

- **Hematology:** Absolute neutrophil count (neutrophil), total leukocytes (Leukocytes), hemoglobin (only do the grading for Anemia, no grading for Hemoglobin increased), platelet count, Lymphocyte.
- **Coagulation:** International normalized ratio.
- **Chemistry:** Alanine aminotransferase albumin, alkaline phosphatase, aspartate aminotransferase, total bilirubin, creatinine, gamma-glutamyl transferase, glucose (only do the grading the Hypoglycemia, no grading for Hyperglycemia), creatine kinase.

Actual values and changes from baseline (screening) in hematology, coagulation, clinical chemistry, and urinalysis will be summarized by treatment.

Shift tables for hematology, clinical chemistry and coagulation from baseline CTCAE toxicity for each visit and to the maximum CTCAE grade on treatment for each parameter will be provided. Participants with both a non-missing baseline and at least one non-missing post-baseline grade will be included in the shift tables. Unscheduled data will be included in the worst case across all scheduled and unscheduled visits after the first dose of study treatment. This means that if there are CTCAE grades derived from both unscheduled and scheduled visits data per test per participant then the highest grade will be summarized.

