14. Changes from Analysis Planned in Protocol

Not Applicable.

This document is confidential.

15. Reference List

This document is confidential.

16. Quality Control

SAS programs are developed to produce output such as analysis data sets, summary tables, data listings, figures or statistical analyses. An overview of the development of programs is detailed in Syneos Health Developing Statistical Programs SOP (3907).

Syneos Health Developing Statistical Programs SOP (3907), Conducting the Transfer of Biostatistical Deliverables SOP (3908) and the SAS Programming and Validation Plan describes the quality control procedures that are performed for all SAS programs and output. Quality control is defined here as the operational techniques and activities undertaken to verify that the SAS programs produce the output by checking for their logic, efficiency and commenting and by review of the produced output.

Syneos Health SOP Pharmacokinetic and Related Data Analysis (3913) describes the process for the interaction between the Biostatistics and Pharmacokinetics departments for the analysis of pharmacokinetic and pharmacodynamic data.

This document is confidential.

ALXN1820-HV-101_Final_Version_SAP_2.0_28 Nov2022_XJ_SS_JW

Final Audit Report

2022-11-30

Created:	2022-11-30
By:	[REDACTED]
Status:	Signed
Transaction ID:	[REDACTED]

"ALXN1820-HV-101_Final_Version_SAP_2.0_28Nov2022_XJ_S S_JW" History

-  Document created by [REDACTED]
2022-11-30 - 1:16:47 PM GMT- IP address: [REDACTED]
-  Document emailed to [REDACTED] for signature
2022-11-30 - 1:18:01 PM GMT
-  Document emailed to [REDACTED] for signature
2022-11-30 - 1:18:01 PM GMT
-  Document emailed to [REDACTED] for signature
2022-11-30 - 1:18:02 PM GMT
-  Email viewed by [REDACTED]
2022-11-30 - 1:18:52 PM GMT- IP address: [REDACTED]
-  Signer [REDACTED] entered name at signing as [REDACTED]
2022-11-30 - 1:19:26 PM GMT- IP address: [REDACTED]
-  [REDACTED] verified identity with Adobe Acrobat Sign authentication
2022-11-30 - 1:19:28 PM GMT
-  Document e-signed by [REDACTED]
Signing reason: I am the author
Signature Date: 2022-11-30 - 1:19:28 PM GMT - Time Source: server- IP address: [REDACTED]
-  Signer [REDACTED] entered name at signing as [REDACTED]
2022-11-30 - 1:20:20 PM GMT- IP address: [REDACTED]

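### Creatinine is graded against ULN only, so a participant with a baseline below two-thirds of ULN can exceed 1.5 x baseline and still be tabulated as Grade 0

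*Protocol*

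**What the plan says.** Protocol Section 9.4.2 states "Laboratory parameter values will be graded according to the Common Terminology Criteria for Adverse Events (CTCAE, v5.0, published 27 Nov 2017" and builds shift tables to the worst post-dose grade from those grades. It makes no exception for creatinine.

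SAP Section 11.2 starts from the same place: "Toxicity grading following the NCI CTCAE grades version 5.0 will also be derived for laboratory variables where applicable". It then makes an exception for creatinine alone: "the criteria based on the upper limit of normal (ULN) will be used (changes compared to the baseline value will not be used". Its example cites CTCAE Grade 1 as above ULN up to 1.5 x ULN, or above 1 up to 1.5 x baseline, and says that only the ULN "criterion will be used (and not the baseline criterion" applies. The resulting grades feed "Shift tables for hematology, clinical chemistry and coagulation from baseline CTCAE toxicity for each visit and to the maximum CTCAE grade on treatment".

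Protocol Section 5.2, criterion 19, excludes anyone with "Serum creatinine greater than the upper limit of normal (ULN) of the reference range of the testing laboratory at Screening or on Day -1". SAP Section 14, headed "Changes from Analysis Planned in Protocol", reads as not applicable.

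**The concern.** Clinical laboratory results are part of the primary safety endpoint (SAP Section 5.1), and the shift and worst-grade tables are where a reader looks for individual laboratory cases. Everyone enters with creatinine at or below ULN. A rise that stays within the reference range can therefore be registered only by a criterion that refers to the participant's own baseline, and the SAP removes exactly those for creatinine. The omission can lower a tabulated grade but never raise one.

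The plan handles QT differently. Protocol Section 9.4.2.1 and SAP Section 11.4 count participants above absolute limits and also those with increases of more than 30 and 60 msec from their own baseline. Creatinine has no equivalent count.

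**Working it through.** The plan gives no figure on this point to reproduce. The check is arithmetic on the grading rule, followed by a look at which other outputs cover the gap.

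**Inputs.** ULN-only grading for creatinine, and the Grade 1 wording that the SAP cites (SAP Section 11.2). Entry creatinine at or below ULN (Protocol Section 5.2, criterion 19).

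**Rule.** Let f = baseline / ULN, so f ≤ 1. After an r-fold rise the value is r x f x ULN. Under the SAP it is Grade 0 while r x f ≤ 1, that is, while r ≤ 1/f. A Grade 0 value above 1.5 x baseline needs 1/f > 1.5, so f < 2/3.

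| Baseline (x ULN) | Largest rise still Grade 0 (1/f) | Value at 1.5 x baseline (x ULN) | Can exceed 1.5 x baseline at Grade 0? |
|---|---|---|---|
| 0.50 | 2.00-fold | 0.75 | yes |
| 0.60 | 1.67-fold | 0.90 | yes |
| 0.65 | 1.54-fold | 0.975 | yes |
| 2/3 | 1.50-fold | 1.00 | no |
| 0.80 | 1.25-fold | 1.20 | no |
| 1.00 | 1.00-fold | 1.50 | no |

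For example, a rise from 0.55 to 0.99 x ULN is 0.99 / 0.55 = 1.80-fold and is Grade 0. From 0.80 x ULN, by contrast, a 1.5-fold rise reaches 1.20 x ULN and is graded.

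**Other planned outputs.**
- *Normal-range shift table* (SAP Section 11.2): limited to tests that CTCAE cannot grade. Creatinine is on the gradable list, so it is left out.
- *Change-from-baseline summary* (SAP Sections 7.1 and 11.2): reports the maximum, but as an absolute change that is not tied to the baseline it came from. In units of ULN, 0.50 to 0.80 and 0.70 to 1.00 are both +0.30, yet they are 0.80 / 0.50 = 1.60-fold and 1.00 / 0.70 = 1.43-fold.
- *Unscheduled values*: SAP Section 7.4 leaves them out of summaries, while SAP Section 11.2 includes them in the worst-grade table. An in-range peak at an unscheduled repeat thus appears in the worst-grade table as Grade 0, is absent from the continuous summary, and can be found only in the full listing.
- *Separate listing of abnormal results* (SAP Section 11.2): a value within range would not ordinarily appear.

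**How many participants could be affected (assumption).** The documents give no creatinine distribution. Suppose that baseline creatinine is normal, that the reference range is its central 95%, and that values above ULN are cut off. With lower limit / ULN = k, the mean is (1 + k)/2 and the SD is (1 − k)/(2 x 1.96). The share p is P(f < 2/3) / P(f < 1). The chance of at least one such participant among 6 active is 1 − (1 − p)^6.

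| k | Mean | SD | p | At least 1 of 6 |
|---|---|---|---|---|
| 0.4 | 0.70 | 0.153 | 42% | 96% |
| 0.5 | 0.75 | 0.128 | 26% | 84% |
| 0.6 | 0.80 | 0.102 | 10% | 46% |

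These are chances that a cohort contains someone whose baseline is low enough for the gap to exist. They are not chances that a rise occurs.

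**The case against.** The strongest reply is that little is hidden. In a cohort of six active participants, one large rise at a scheduled visit will usually be the reported maximum change. All results are listed. Protocol Section 8.2.4 requires the investigator to record clinically relevant laboratory changes as adverse events, Section 10.3.1 includes those that worsen from baseline, and Section 10.3.3 has the investigator grade them by CTCAE without the SAP's creatinine rule. Such an event would reach the primary endpoint through the adverse event tables. This stands, and it limits the harm to the graded laboratory tables.

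The SAP also states its rule openly. Protocol Section 9.4 calls itself a high-level summary, and Section 9.4.2 describes baseline grades in the shift tables by reference ranges, which fits a ULN-based approach. Dropping the Grade 1 baseline limb is defensible, because as cited it would grade any upward fluctuation. This also stands. But it explains leaving out rises up to 1.5 x baseline. It does not explain having no count of larger ones, and the SAP gives no reason.

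A reader might infer three stronger things that the documents do not support:
- *That every participant who enters at or below ULN is affected.* Only baselines strictly below two-thirds of ULN are.
- *That the safety analysis as a whole would miss a renal signal.* The maximum, the listings and adverse event reporting remain. The documents name no renal risk, and the stopping rules in Protocol Section 7.2 contain no creatinine-specific limit that this would alter.
- *That these values should carry a particular higher grade.* The documents reproduce only the Grade 1 criterion. What can be said is that a value above 1.5 x baseline lies beyond the baseline band the SAP cites for Grade 1.

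**Conclusion.** The point holds within limits. The SAP narrows the grading standard that the protocol names, for creatinine only, without declaring it in Section 14. As a result, rises of more than 1.5-fold, up to 1/f-fold, are tabulated as Grade 0 for participants with f below 2/3. That much follows from the documents alone. How many participants fall in this range is unknown; the 10% to 42% above depends on the assumed distribution.

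The gap is a missing count in a primary-safety display. It affects descriptive reporting only: safety analyses are not inferential, and no sample size, power or error rate changes.

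**What to change.** In SAP Section 11.2, keep the ULN-based creatinine grading and the exclusion of the Grade 1 band above 1 up to 1.5 x baseline. Beside the creatinine shift table, add the number and percentage of participants, by cohort and arm, with any post-dose creatinine above 1.5 x baseline, counting scheduled and unscheduled values. State which baseline the ratio uses: SAP Section 7.2 defines the last value before dosing, while Section 11.2 labels the laboratory baseline as screening.

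Alternatively, apply whatever baseline criteria CTCAE v5.0 gives above 1.5 x baseline and tabulate the worse of the two grades. The sponsor would need to take those criteria from CTCAE itself, since neither document reproduces them.

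Under either option, record the remaining departure from Protocol Section 9.4.2 and its reason in SAP Section 14.

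The cost is one SAP rule and a small program change, with no new data collection. The downside is that a participant with a very low baseline may be flagged for a modest absolute rise; showing the baseline and peak values beside each flagged case lets the reader judge that.

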9.4.2.1. ECG Analysis

Intensive cardiac assessments will be performed in the Safety Population using food effects on ECG to establish assay sensitivity. Analysis of drug related QT/QTc interval changes relative to plasma PK concentrations will be conducted on all dose regimens. The principles of this analysis follow the statistical methods described by Garnett et al. (Garnett, 2018). The ECG utilized for this analysis requires adjudication by qualified cardiologists in accordance with principles set out in the International Conference on Harmonisation (ICH) E14 guideline and subsequent Q&A documents. All ECG recordings will be in triplicate and compliant with the correct recording and manual adjudication of ECG in thorough QT/QTc studies. The ECG analyses will be based on adjudicated selected triplicates from each time point.

The ECG parameters will be measured at the specified time points, including heart rate, PR, RR, QRS, QT, and corrected QTcF intervals. The average of the triplicate ECG readings at the time points collected will be calculated, and changes from pretreatment baseline values will be assessed by each cohort and treatment arm.

An outlier analysis will be performed that will summarize the absolute count, frequency and percentage of participants who meet any of the following outlier criteria at each visit by cohort and treatment arm:

- QT, QTcF interval > 450 msec
- QT, QTcF interval > 480 msec
- QT, QTcF interval > 500 msec
- QT, QTcF interval increases from baseline > 30 msec

- QT, QTcF interval increases from baseline > 60 msec

Detailed analysis will be specified in the SAP or a separate ECG analysis plan.

